6.5 PK ANALYSES

The PK analysis population will consist of patients with sufficient data to enable estimation of key parameters (e.g., area under the concentration–time curve [AUC], time to maximum concentration, maximum concentration [C_{max}], and terminal half-life).

Individual and mean plasma of each study drugs concentration versus time data will be tabulated and plotted by dose level. The plasma pharmacokinetics of each study drugs will be summarized by estimating total exposure (AUC), C_{max} , total clearance, volume of distribution at steady-state, and terminal half-life (as appropriate for data collected). Estimates for these parameters will be tabulated and summarized (mean, standard deviation, coefficient of variation, median, minimum, and maximum). Inter-patient variability and drug accumulation will be evaluated.

Additional PK analyses will be conducted as appropriate.

6.6 BIOMARKER ANALYSES

Biomarker results will be analyzed for association with patient clinical characteristics, prognostic and predictive value, as well as outcome, prevalence, and correlation with other biomarkers.

Data may be analyzed in the context of this study and in aggregate with data from other studies.

6.7 HEALTH STATUS UTILITY ANALYSES

Change from baseline in EQ-5D-5L health utility index-based and VAS scores will be calculated at specified timepoints.

6.8 INTERIM ANALYSES

Optional interim safety and/or efficacy data review may be carried out by an internal monitoring committee (IMC) that includes Sponsor members at the discretion of the Medical Monitor. The decision to conduct such an analysis and the corresponding timing will be documented in the Sponsor's trial master file prior to the conduct of the interim analysis. In particular, given the hypothesis-generating nature of this study, the Sponsor may choose to conduct interim efficacy analyses for early stopping (futility) by using observed proportion of patients achieving complete response (e.g., predictive probability that this trial will have a positive outcome if carried out to completion based on historical control data available at the time of analysis).

Further details regarding the rules and guidelines of the data review will be provided in an IMC charter if applicable.

7. DATA COLLECTION AND MANAGEMENT

7.1 DATA QUALITY ASSURANCE

The Sponsor will be responsible for data management of this study, including quality checking of the data. Data entered manually will be collected via EDC through use of eCRFs. Sites will be responsible for data entry into the EDC system. In the event of discrepant data, the Sponsor will request data clarification from the sites, which the sites will resolve electronically in the EDC system.

The Sponsor will produce an EDC Study Specification document that describes the quality checking to be performed on the data. Central laboratory data will be sent directly to the Sponsor, using the Sponsor's standard procedures to handle and process the electronic transfer of these data.

eCRFs and correction documentation will be maintained in the EDC system's audit trail. System backups for data stored by the Sponsor and records retention for the study data will be consistent with the Sponsor's standard procedures.

7.2 ELECTRONIC CASE REPORT FORMS

eCRFs are to be completed through use of a Sponsor-designated EDC system. Sites will receive training and have access to a manual for appropriate eCRF completion. eCRFs will be submitted electronically to the Sponsor and should be handled in accordance with instructions from the Sponsor.

All eCRFs should be completed by designated, trained site staff. eCRFs should be reviewed and electronically signed and dated by the investigator or a designee.

At the end of the study, the investigator will receive patient data for his or her site in a readable format that must be kept with the study records. Acknowledgement of receipt of the data is required.

7.3 SOURCE DATA DOCUMENTATION

Study monitors will perform ongoing source data verification and review to confirm that critical protocol data (i.e., source data) entered into the eCRFs by authorized site personnel are accurate, complete, and verifiable from source documents.

Source documents (paper or electronic) are those in which patient data are recorded and documented for the first time. They include, but are not limited to, hospital records, clinical and office charts, laboratory notes, memoranda, patient-reported outcomes, evaluation checklists, pharmacy dispensing records, recorded data from automated instruments, copies of transcriptions that are certified after verification as being accurate and complete, microfiche, photographic negatives, microfilm or magnetic media, X-rays, patient files, and records kept at pharmacies, laboratories, and medico-technical departments involved in a clinical trial.

Before study initiation, the types of source documents that are to be generated will be clearly defined in the Trial Monitoring Plan. This includes any protocol data to be entered directly into the eCRFs (i.e., no prior written or electronic record of the data) and considered source data.

Source documents that are required to verify the validity and completeness of data entered into the eCRFs must not be obliterated or destroyed and must be retained per the policy for retention of records described in Section 7.5.

To facilitate source data verification and review, the investigators and institutions must provide the Sponsor direct access to applicable source documents and reports for trial-related monitoring, Sponsor audits, and IRB/EC review. The study site must also allow inspection by applicable health authorities.

7.4 USE OF COMPUTERIZED SYSTEMS

When clinical observations are entered directly into a study site's computerized medical record system (i.e., in lieu of original hardcopy records), the electronic record can serve as the source document if the system has been validated in accordance with health authority requirements pertaining to computerized systems used in clinical research. An acceptable computerized data collection system allows preservation of the original entry of data. If original data are modified, the system should maintain a viewable audit trail that shows the original data as well as the reason for the change, name of the person making the change, and date of the change.

7.5 RETENTION OF RECORDS

Records and documents pertaining to the conduct of this study and the distribution of IMP, including eCRFs, paper PRO data, Informed Consent Forms, laboratory test results, and medication inventory records, must be retained by the Principal Investigator for at least 15 years after completion or discontinuation of the study or for the length of time required by relevant national or local health authorities, whichever is longer. After that period of time, the documents may be destroyed, subject to local regulations.

No records may be disposed of without the written approval of the Sponsor. Written notification should be provided to the Sponsor prior to transferring any records to another party or moving them to another location.

8. ETHICAL CONSIDERATIONS

8.1 COMPLIANCE WITH LAWS AND REGULATIONS

This study will be conducted in full conformance with the ICH E6 guideline for Good Clinical Practice and the principles of the Declaration of Helsinki, or the laws and regulations of the country in which the research is conducted, whichever affords the greater protection to the individual. The study will comply with the requirements of the ICH E2A guideline (Clinical Safety Data Management: Definitions and Standards for

Expedited Reporting). Studies conducted in the United States or under a U.S. Investigational New Drug (IND) Application will comply with U.S. Food and Drug Administration regulations and applicable local, state, and federal laws. Studies conducted in the European Union or European Economic Area will comply with the E.U. Clinical Trial Directive (2001/20/EC).

8.2 INFORMED CONSENT

The Sponsor's sample Informed Consent Form (and ancillary sample Informed Consent Forms such as a Child's Informed Assent Form or Mobile Nursing Informed Consent Form, if applicable) will be provided to each site. If applicable, it will be provided in a certified translation of the local language. The Sponsor or its designee must review and approve any proposed deviations from the Sponsor's sample Informed Consent Forms or any alternate consent forms proposed by the site (collectively, the "Consent Forms") before IRB/EC submission. The final IRB/EC-approved Consent Forms must be provided to the Sponsor for health authority submission purposes according to local requirements.

If applicable, the Informed Consent Form will contain separate sections for any optional procedures. The investigator or authorized designee will explain to each patient the objectives, methods, and potential risks associated with each optional procedure. Patients will be told that they are free to refuse to participate and may withdraw their consent at any time for any reason. A separate, specific signature will be required to document a patient's agreement to participate in optional procedures. Patients who decline to participate will not provide a separate signature.

The Consent Forms must be signed and dated by the patient or the patient's legally authorized representative before his or her participation in the study. The case history or clinical records for each patient shall document the informed consent process and that written informed consent was obtained prior to participation in the study.

The Consent Forms should be revised whenever there are changes to study procedures or when new information becomes available that may affect the willingness of the patient to participate. The final revised IRB/EC-approved Consent Forms must be provided to the Sponsor for health authority submission purposes.

Patients must be re-consented to the most current version of the Consent Forms (or to a significant new information/findings addendum in accordance with applicable laws and IRB/EC policy) during their participation in the study. For any updated or revised Consent Forms, the case history or clinical records for each patient shall document the informed consent process and that written informed consent was obtained using the updated/revised Consent Forms for continued participation in the study.

A copy of each signed Consent Form must be provided to the patient or the patient's legally authorized representative. All signed and dated Consent Forms must remain in

each patient's study file or in the site file and must be available for verification by study monitors at any time.

For sites in the United States, each Consent Form may also include patient authorization to allow use and disclosure of personal health information in compliance with the U.S. Health Insurance Portability and Accountability Act (HIPAA) of 1996. If the site utilizes a separate Authorization Form for patient authorization for use and disclosure of personal health information under the HIPAA regulations, the review, approval, and other processes outlined above apply except that IRB review and approval may not be required per study site policies.

8.3 INSTITUTIONAL REVIEW BOARD OR ETHICS COMMITTEE

This protocol, the Informed Consent Forms, any information to be given to the patient, and relevant supporting information must be submitted to the IRB/EC by the Principal Investigator and reviewed and approved by the IRB/EC before the study is initiated. In addition, any patient recruitment materials must be approved by the IRB/EC.

The Principal Investigator is responsible for providing written summaries of the status of the study to the IRB/EC annually or more frequently in accordance with the requirements, policies, and procedures established by the IRB/EC. Investigators are also responsible for promptly informing the IRB/EC of any protocol amendments (see Section 9.6).

In addition to the requirements for reporting all adverse events to the Sponsor, investigators must comply with requirements for reporting serious adverse events to the local health authority and IRB/EC. Investigators may receive written IND safety reports or other safety-related communications from the Sponsor. Investigators are responsible for ensuring that such reports are reviewed and processed in accordance with health authority requirements and the policies and procedures established by their IRB/EC, and archived in the site's study file.

8.4 CONFIDENTIALITY

The Sponsor maintains confidentiality standards by coding each patient enrolled in the study through assignment of a unique patient identification number. This means that patient names are not included in data sets that are transmitted to any Sponsor location.

Patient medical information obtained by this study is confidential and may be disclosed to third parties only as permitted by the Informed Consent Form (or separate authorization for use and disclosure of personal health information) signed by the patient, unless permitted or required by law.

Medical information may be given to a patient's personal physician or other appropriate medical personnel responsible for the patient's welfare, for treatment purposes.

Given the complexity and exploratory nature of exploratory biomarker analyses, data derived from these analyses will generally not be provided to study investigators or patients unless required by law. The aggregate results of any conducted research will be available in accordance with the effective Sponsor policy on study data publication (see Section 9.5).

Data generated by this study must be available for inspection upon request by representatives of national and local health authorities, Sponsor monitors, representatives, and collaborators, and the IRB/EC for each study site, as appropriate.

Study data may be submitted to government or other health research databases or shared with researchers, government agencies, companies, or other groups that are not participating in this study. These data may be combined with or linked to other data and used for research purposes, to advance science and public health, or for analysis, development, and commercialization of products to treat and diagnose disease. In addition, redacted clinical study reports and other summary reports will be provided upon request.

8.5 FINANCIAL DISCLOSURE

Investigators will provide the Sponsor with sufficient, accurate financial information in accordance with local regulations to allow the Sponsor to submit complete and accurate financial certification or disclosure statements to the appropriate health authorities. Investigators are responsible for providing information on financial interests during the course of the study and for 1 year after completion of the study (see definition of end of study in Section 3.2).

9. STUDY DOCUMENTATION, MONITORING, AND ADMINISTRATION

9.1 STUDY DOCUMENTATION

The investigator must maintain adequate and accurate records to enable the conduct of the study to be fully documented, including, but not limited to, the protocol, protocol amendments, Informed Consent Forms, and documentation of IRB/EC and governmental approval. In addition, at the end of the study, the investigator will receive the patient data, including an audit trail containing a complete record of all changes to data.

9.2 PROTOCOL DEVIATIONS

The investigator should document and explain any protocol deviations. The investigator should promptly report any deviations that might have an impact on patient safety and data integrity to the Sponsor and to the IRB/EC in accordance with established IRB/EC policies and procedures. The Sponsor will review all protocol deviations and assess whether any represent a serious breach of Good Clinical Practice guidelines and require reporting to health authorities. As per the Sponsor's standard operating procedures,

prospective requests to deviate from the protocol, including requests to waive protocol eligibility criteria, are not allowed.

9.3 SITE INSPECTIONS

Site visits will be conducted by the Sponsor or an authorized representative for inspection of study data, patients' medical records, and eCRFs. The investigator will permit national and local health authorities; Sponsor monitors, representatives, and collaborators; and the IRBs/ECs to inspect facilities and records relevant to this study.

9.4 ADMINISTRATIVE STRUCTURE

This trial will be sponsored and managed by F. Hoffmann-La Roche Ltd. The Sponsor will provide clinical operations management, data management, and medical monitoring.

An EDC system will be used for this study. An IxRS will be used to assign patient numbers. A central laboratory will be used for a subset of laboratory assessments as specified in Section 4.5.7; otherwise, local laboratories will be used. Data from this study will be shared with an expert scientific committee that will provide scientific input for the benefit–risk assessment.

9.5 DISSEMINATION OF DATA AND PROTECTION OF TRADE SECRETS

Regardless of the outcome of a trial, the Sponsor is dedicated to openly providing information on the trial to healthcare professionals and to the public, at scientific congresses, in clinical trial registries of the U.S. National Institutes of Health and the European Medicines Agency, and in peer-reviewed journals. The Sponsor will comply with all requirements for publication of study results. Study data may be shared with others who are not participating in this study, and redacted clinical study reports and other summary reports will be provided upon request (see Section 8.4 for more details). For more information, refer to the Roche Global Policy on Sharing of Clinical Trials Data at the following web site:

www.roche.com/roche_global_policy_on_sharing_of_clinical_study_information.pdf

The results of this study may be published or presented at scientific congresses. For all clinical trials in patients involving an IMP for which a marketing authorization application has been filed or approved in any country, the Sponsor aims to submit a journal manuscript reporting primary clinical trial results within 6 months after the availability of the respective Clinical Study Report. In addition, for all clinical trials in patients involving an IMP for which a marketing authorization application has been filed or approved in any country, the Sponsor aims to publish results from analyses of additional endpoints and exploratory data that are clinically meaningful and statistically sound.

The investigator must agree to submit all manuscripts or abstracts to the Sponsor prior to submission for publication or presentation. This allows the Sponsor to protect

proprietary information and to provide comments based on information from other studies that may not yet be available to the investigator.

In accordance with standard editorial and ethical practice, the Sponsor will generally support publication of multicenter trials only in their entirety and not as individual center data. In this case, a coordinating investigator will be designated by mutual agreement.

Authorship will be determined by mutual agreement and in line with International Committee of Medical Journal Editors authorship requirements. Any formal publication of the study in which contribution of Sponsor personnel exceeded that of conventional monitoring will be considered as a joint publication by the investigator and the appropriate Sponsor personnel.

Any inventions and resulting patents, improvements, and/or know-how originating from the use of data from this study will become and remain the exclusive and unburdened property of the Sponsor, except where agreed otherwise.

Appendix 1: Schedule of Activities

**Appendix 1
Schedule of Activities**

Table 1: Induction

| Assessment/Procedure | Screening ^a | Induction (28-Day Cycle) up to 2 Cycles | | | | | | | | | |
|--|------------------------|---|----|----|----|----|----|----|-----|-----|----------------|
| | Days -14 to -1 | D1 | D2 | D3 | D4 | D5 | D7 | D8 | D15 | D22 | D28 |
| | | | | | | | | | | | |
| Informed consent(s) ^b | x | | | | | | | | | | |
| Serum pregnancy test ^c | x | | | | | | | | | | |
| Demographics, medical history, determination of cytogenetic and molecular risk, physical examination, height, chest X-ray (or chest CT) ^d | x | | | | | | | | | | |
| Vital signs ^e , weight, ECOG performance status | x | x | | | | | | x | x | x | x ^f |
| Triplicate 12-Lead ECG ^g | x | x | x | x | | x | | | | | |
| MUGA or ECHO | x | | | | | | | | | | |
| Coagulation (INR, aPTT [or PTT], and PT) | x | | | | | | | | | | |
| Targeted physical examination ^h | | x | | | | | | x | x | x | x ^f |
| Urinalysis | x | x | | | | | | | | | |
| Hepatitis B and C testing ⁱ | x | | | | | | | | | | |
| C. difficile toxin and toxin-producing C. difficile in stool | x | | | | | | | | | | |
| Chemistry ^j | x | x | x | | | x | | x | x | x | x ^f |
| Hematology ^j | x | x | x | | | x | | x | x | x | x ^f |
| FACIT-Fatigue, EORTC Item Library, PRO-CTCAE ^k | | x | | | | | | | | | |

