4.5.10.4 PRO-CTCAE

The PRO-CTCAE is a validated item bank that is used to characterize presence, frequency, severity, and interference with daily function of 78 patient-reportable symptomatic treatment toxicities (Basch et al. 2014; Dueck et al. 2015). The PRO-CTCAE contains 124 questions that are rated on either a 5-point Likert-type scale (frequency, severity, and interference) or dichotomously (presence/absence). Included treatment toxicity terms can be subjective, with or without observable components (e.g., vomiting and nausea, respectively) or primarily observable with subjective components (e.g., rash). The standard PRO-CTCAE recall period is "the past 7 days."

A subset of three symptoms (nausea, vomiting, diarrhea) deemed most applicable to treatment with idasanutlin was selected for this study based on known adverse events. The five items assessing these symptoms will be used to characterize the patient experience of symptomatic adverse events (see [Appendix 15](#)).

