- ^k PRO questionnaires need to be self-administered before the patient receives any information on disease status and prior to the administration of study treatment. Completion of PROs should occur prior to the performance of non-PRO assessments whenever possible. PRO assessments include the FACIT-Fatigue, EORTC QLQ-C30, EORTC Item Library symptoms, PRO-CTCAE, and EQ-5D-5L.
- ^l Only first cycle of induction.
- ^m At screening, bone marrow examination will require biopsy if an aspirate is not evaluable to confirm the AML diagnosis. For HMRA during study, bone marrow aspirates are required, but bone marrow biopsies may be performed at the discretion of the investigator.

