Appendix 1: Schedule of Activities (cont.)

Table 2: Chemotherapy Consolidation

| Assessment/Procedure | Consolidation (28-Day Cycle) up to 4 Cycles | | | | | | | | |
|--|---|----|----|----|----|----|-----|-----|------------------|
| | D1 | D2 | D3 | D4 | D5 | D8 | D15 | D22 | D28 |
| Vital Signs ^a , weight, ECOG performance status | x | | | | | x | x | x | x ^b |
| Single 12-Lead ECG ^c | x | x | x | | x | | | | |
| Targeted physical examination ^d | x | | | | | x | x | x | x ^b |
| Urinalysis | x | | | | | | | | |
| Biochemistry ^e | x | x | | | x | x | x | x | x ^b |
| Hematology ^e | x | x | | | x | x | x | x | x ^b |
| FACIT-Fatigue, EORTC Item Library, PRO-CTCAE, EORTC QLQ-C30, EQ-5D-5L ^f | x | | | | | | | | |
| HMRA | | | | | | | | | x ^b |
| Bone marrow sampling for HMRA ^g | | | | | | | | | x ^b |
| Bone marrow sampling for MRD/Flow, EDTA, PAXgene [®] ^h | | | | | | | | | x ^b |
| Whole blood sampling for EDTA and clinical | x | | | | | | | | x ^{b,i} |
| RBR sampling, blood serum and plasma (optional) | x | | | | | | | | |
| PK sampling | Refer to Appendix 2 | | | | | | | | |
| Concomitant medications | To be recorded continually; see Section 4.4 | | | | | | | | |
| Adverse events | To be assessed continually; see Section 5.3.1 | | | | | | | | |
| Cytarabine (1.5 g/m ² IV) ^j | x | x | x | x | x | | | | |
| Idasanutlin (PO QD) ^j | x | x | x | x | x | | | | |

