Appendix 1: Schedule of Activities (cont.)

Table 3: Maintenance in the Dose-Escalation Cohort and Expansion

| Assessment/Procedure | Maintenance (28-Day Cycle; ± 2 days) All Cycles | | | | | | |
|--|---|----|----|----|----|----------------|----------------|
| | D1 | D2 | D3 | D4 | D5 | D15 | D28 (Q3M) |
| Vital signs ^a , weight, ECOG performance status | x | | | | | | |
| Single 12-Lead ECG ^b | x | | | | | | |
| Targeted physical examination ^c | x | | | | | | |
| Urinalysis | x | | | | | | |
| FACIT-Fatigue, EORTC Item Library, EQ-5D-5L ^d | x ^e | | | | | | |
| PRO-CTCAE, EORTC QLQ-C30 ^d | x | | | | | | |
| Biochemistry ^f | x | | | | | x ^g | |
| Hematology ^f | x | | | | | x ^g | |
| HMRA | x | | | | | | x |
| Bone marrow sampling for HMRA ^h | x ⁱ | | | | | | x |
| RBR sampling Blood serum, plasma (optional) | x | | | | | | |
| Bone marrow sampling for MRD/Flow, EDTA, PAXgene [®] ^j | x ⁱ | | | | | | x |
| Whole blood sampling for EDTA and clinical | x | | | | | | x ^k |
| PK sampling | Refer to Appendix 2 | | | | | | |
| Concomitant medications | To be recorded continually; see Section 4.4 | | | | | | |
| Adverse events | To be assessed continually; see Section 5.3.1 | | | | | | |
| Idasanutlin (PO QD) ^l | x | x | x | x | x | | |

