Appendix 1: Schedule of Activities (cont.)

Table 4: Maintenance in Post-Consolidation Cohort

| Assessment/Procedure | Screening ^a | Maintenance (28-Day Cycle; ± 2 days) All Cycles | | | | | | |
|--|------------------------|---|----|----|----|----|----------------|-----------|
| | Days – 14 to – 1 | D1 | D2 | D3 | D4 | D5 | D15 | D28 (Q3M) |
| Informed consent(s) ^b | x | | | | | | | |
| Demographics, medical history, determination of cytogenetic and molecular risk, physical examination, height, chest X-ray (or chest CT) ^c | x | | | | | | | |
| MUGA or ECHO | x | | | | | | | |
| Urinalysis | x | | | | | | | |
| Hepatitis B and C testing ^d | x | | | | | | | |
| C. difficile toxin and toxin-producing C. difficile in stool | x | | | | | | | |
| Serum pregnancy test ^e | x | | | | | | | |
| Coagulation (INR, aPTT [or PTT], and PT) | x | | | | | | | |
| Vital signs ^f , weight, ECOG performance status | x | x | | | | | | |
| Single 12-Lead ECG ^g | x | x | | | | | | |
| Targeted physical examination ^h | | x | | | | | | |
| Urinalysis | x | x | | | | | | |
| FACIT-Fatigue, EORTC Item Library, EQ-5D-5L ⁱ | | x ^j | | | | | | |
| PRO-CTCAE, EORTC QLQ-C30 ⁱ | | x | | | | | | |
| Biochemistry ^k | x | x | | | | | x ^l | |

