Appendix 1: Schedule of Activities (cont.)

Table 5: Post-Treatment Phase

| Assessment/Procedure | Study Drug Discontinuation/Early Termination Visit 28 Days after Last Dose of Study Drug | Post-Tx Follow-Up Period | | Survival Follow-Up Period (Q3M) ^b |
|--|---|--------------------------------|--------------------------------|--|
| | | Q1M up to 2 Years ^a | Q6M up to 2 Years ^a | |
| Serum pregnancy test | x | | | |
| Triplicate 12-lead ECG | x | | | |
| Biochemistry | x | x | | |
| Hematology | x | x | | |
| Urinalysis | x | | | |
| HMRA | x | | x | |
| Bone marrow sampling for HMRA ^c | x | | x | |
| Bone marrow sampling (MRD/Flow, EDTA, PAXgene [®]) ^d | x | | x | |
| Whole blood sampling (EDTA, clinical) | x | x | | |
| FACIT-Fatigue, EORTC Item Library, PRO-CTCAE, EORTC QLQ-C30, EQ-5D-5L ^e | x | | | |
| Concomitant medications | x | | | |
| Adverse events | x | x | | |
| New leukemia treatment | | x | | x |
| Survival follow-up | | | | x |

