Appendix 12 FACIT-Fatigue

FACIT Fatigue Scale (Version 4)

Below is a list of statements that other people with your illness have said are important. Please circle or mark one number per line to indicate your response as it applies to the past 7 days.

| | | Not at all | A little bit | Some- what | Quite a bit | Very much |
|------|--|---------------|-----------------|---------------|----------------|--------------|
| H07 | I feel fatigued | 0 | 1 | 2 | 3 | 4 |
| H112 | I feel weak all over | 0 | 1 | 2 | 3 | 4 |
| An1 | I feel listless ("washed out") | 0 | 1 | 2 | 3 | 4 |
| An2 | I feel tired..... | 0 | 1 | 2 | 3 | 4 |
| An3 | I have trouble starting things because I am tired..... | 0 | 1 | 2 | 3 | 4 |
| An4 | I have trouble finishing things because I am tired | 0 | 1 | 2 | 3 | 4 |
| An5 | I have energy..... | 0 | 1 | 2 | 3 | 4 |
| An7 | I am able to do my usual activities..... | 0 | 1 | 2 | 3 | 4 |
| An8 | I need to sleep during the day | 0 | 1 | 2 | 3 | 4 |
| An12 | I am too tired to eat..... | 0 | 1 | 2 | 3 | 4 |
| An14 | I need help doing my usual activities | 0 | 1 | 2 | 3 | 4 |
| An15 | I am frustrated by being too tired to do the things I want to do | 0 | 1 | 2 | 3 | 4 |
| An16 | I have to limit my social activity because I am tired..... | 0 | 1 | 2 | 3 | 4 |

Appendix 15

Patient-Reported Outcomes Common Terminology Criteria for Adverse Events (PRO-CTCAE)

NCI PRO-CTCAE™ ITEMS

Item Library Version 1.0

English

Form created on 26 May 2018

As individuals go through treatment for their cancer they sometimes experience different symptoms and side effects. For each question, please check or mark an in the one box that best describes your experiences over the past 7 days...

| | | | | | |
|----|--|------------------------------|------------------------------------|----------------------------------|---|
| 1. | In the last 7 days, how OFTEN did you have NAUSEA? | | | | |
| |  Never |  Rarely |  Occasionally |  Frequently |  Almost constantly |
| | In the last 7 days, what was the SEVERITY of your NAUSEA at its WORST? | | | | |
| |  None |  Mild |  Moderate |  Severe |  Very severe |

| | | | | | |
|----|--|------------------------------|------------------------------------|----------------------------------|---|

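### Every scheduled post-baseline PRO-CTCAE form has a 7-day recall that misses the idasanutlin dosing days, so patient-reported acute nausea, vomiting and diarrhea are not captured

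*Combined protocol and SAP*

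**What the plan says.** Section 2.1 lists the presence, frequency, severity and interference of nausea, vomiting and diarrhea, measured by PRO-CTCAE, as a safety endpoint, together with change from baseline. Section 3.3.5 explains that these three symptoms were selected as salient to idasanutlin, and that patients are asked directly because clinicians may under-report symptoms.

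On recall, Section 4.5.10.4 says "The standard PRO-CTCAE recall period is" the past 7 days. The form in Appendix 15 asks for the answer that "best describes your experiences over the past 7 days".

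On timing, Appendix 1 marks the form as follows:

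- **Induction (Table 1):** Day 1 only: "FACIT-Fatigue, EORTC Item Library, PRO-CTCAE ^k | | x".
- **Consolidation (Table 2):** Day 1 only: "FACIT-Fatigue, EORTC Item Library, PRO-CTCAE, EORTC QLQ-C30, EQ-5D-5L ^f | x".
- **Maintenance, dose-escalation and expansion patients (Table 3):** Day 1 only: "PRO-CTCAE, EORTC QLQ-C30 ^d | x". Table 4 (post-consolidation cohort) has the same Day 1 mark. Both tables carry the header "Maintenance (28-Day Cycle; ± 2 days) All Cycles".
- **After treatment (Table 5):** once, at the "Study Drug Discontinuation/Early Termination Visit 28 Days after Last Dose of Study Drug".

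Footnote k to Table 1 adds that "PRO questionnaires need to be self-administered before the patient receives any information on disease status and prior to the administration of study treatment". The consolidation and maintenance tables carry the same footnote. All four treatment tables schedule idasanutlin on Days 1–5.

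Section 6.4 will report the proportion with each symptom and the change from baseline at each timepoint, and the maximum post-baseline score.

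**The concern.** A form with a one-week memory, completed just before the next cycle's first dose, looks back at the end of the preceding cycle. Dosing was at its beginning. The protocol's own text places the symptoms of interest near dosing:

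- Table 6 requires anti-emetic and anti-diarrheal premedication before each idasanutlin dose in induction and consolidation.
- Table 10 has a rule for Grade 3 diarrhea arising on Days 1 to 5.
- Appendix 5 ends loperamide treatment no later than Day 10 of the cycle.
- Section 3.3.5 says quality of life falls most soon after induction starts and recovers afterwards.

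Post-baseline forms would thus sample the recovery rather than the episode. A low maximum score would be read as good tolerability on treatment when the question was never asked about treatment days. No other questionnaire fills the gap: the QLQ-C30 scales kept (Section 4.5.10.2) and the Item Library items (Section 4.5.10.3) contain nothing on nausea, vomiting or diarrhea.

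**Working it through.** The plan states no figure on this point, so there is none to reproduce. The check is a calendar overlap.

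**Inputs**

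- Recall period: 7 days (Section 4.5.10.4, Appendix 15).
- Form timing: Day 1 before dosing, and 28 days after the last dose (Appendix 1, Tables 1–5).
- Idasanutlin: Days 1–5 of each cycle (Appendix 1, Tables 1–4).
- Cycle length: 28 days, with ±2 days in maintenance. Footnote f to Table 1 (D56) and footnote b to Table 2 (D49) are used as extended cycle lengths.
- Number of cycles: up to 2 induction, up to 4 consolidation, 12 maintenance (Tables 1, 4 and 5 of Section 3.1).

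**Recall week of the next Day 1 form**

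For a cycle of L days, the next form is completed on Day L+1 and recalls Days L−6 to L. The week opens (L−6) − 5 = L−11 days after the Day 5 dose.

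| Cycle length L | Days recalled | Gap from Day 5 dose | Dosing days covered |
|---|---|---|---|
| 26 (maintenance, −2) | 20–26 | 15 days | 0 of 5 |
| 28 | 22–28 | 17 days | 0 of 5 |
| 30 (maintenance, +2) | 24–30 | 19 days | 0 of 5 |
| 49 (consolidation extended) | 43–49 | 38 days | 0 of 5 |
| 56 (induction extended) | 50–56 | 45 days | 0 of 5 |

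Reaching Day 5 would need L−6 ≤ 5, that is, a cycle of 11 days or less. Counting the form day in the recall does not help: in a 28-day cycle the window becomes Days 23–29, and Day 29 is the new Day 1 before its dose.

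**Discontinuation form**

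It recalls 28−7 = 21 to 28−1 = 27 days after the last dose. Overlap with dosing: 0.

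**Number of forms**

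- Dose-escalation or expansion, maximum planned course: 2 + 4 + 12 + 1 = 19 forms, less 1 baseline = 18 post-baseline. They cover 0 of (2 + 4 + 12) × 5 = 90 scheduled dosing days.
- Post-consolidation cohort: 12 + 1 − 1 = 12 post-baseline forms, covering 0 of 12 × 5 = 60.

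**Alternative days**

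A form completed on Day d recalls Days d−7 to d−1.

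- Day 8: Days 1–7, 5 of 5 dosing days.
- Day 15: Days 8–14, 0 of 5.
- Day 22: Days 15–21, 0 of 5.
- Day 28: Days 21–27, 0 of 5.

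Of the existing visits after dosing ends, only Day 8 covers the dosing days.

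**The case against.** The strongest reply is that acute gastrointestinal toxicity is well covered elsewhere. Adverse events are assessed continually. Sections 5.3.1 and 5.3.2 have patients asked at each contact how they have felt, and record what they report. Grade ≥ 2 diarrhea is an adverse event of special interest (Section 5.2.3), and Appendix 5 has stools counted during diarrhea. PRO-CTCAE is one descriptive endpoint in a non-randomized study that Section 6.8 calls hypothesis-generating, and Section 6.4 presents it apart from the safety analyses. Day 1 forms also have a use: they show what persists between cycles, such as the diarrhea that Appendix 5 envisages as unresolved at 28 days.

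Much of this stands. Safety detection and dose selection are not at risk, and patient complaints do enter the adverse event record. That record is graded by clinicians, however. It does not supply standardized self-rated frequency and severity, which is what the endpoint promises, and Section 5.3.5.11 says the two sources will not be reconciled. Section 5.1.1.1 reports diarrhea in more than 90% of patients in the earlier AML study, mostly Grades 1 and 2; Grade 1 falls below the special-interest threshold.

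Two limits also stand. The documents give no distribution of onset or duration for these symptoms, so the size of any understatement cannot be calculated. And 18 forms is a maximal course: transplant or fewer cycles reduce the number, and continued maintenance raises it. The coverage per cycle remains 0 of 5.

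**Conclusion.** The concern holds. As scheduled, no post-baseline PRO-CTCAE form reaches a scheduled idasanutlin dosing day: 0 of 5 days per cycle, 0 of 18 forms in a full dose-escalation or expansion course, and 0 of 12 in the post-consolidation cohort. Neither the ±2-day window nor cycle extension changes this. Symptoms that last into, or arise in, the final week of a cycle will register; acute symptoms around dosing will not.

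The counts rest on scheduled dosing. A dose withheld and resumed later in the same cycle could fall nearer the recall week. That the Section 6.4 summaries will understate symptoms around dosing is a judgment, based on the protocol's own expectation that these symptoms cluster near treatment. The schedule should be changed: a listed safety endpoint cannot describe what it was chosen to describe, and the remedy is small.

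**What to change.** 1. **Induction and consolidation:** add the five-item PRO-CTCAE at the existing Day 8 visit of every cycle. No study drug is scheduled that day, so the rule on completion before dosing is not disturbed.
2. **Maintenance (Appendix 1, Tables 3 and 4):** there is no Day 8 visit. Give patients a paper form to complete and date on Day 8 in at least Cycles 1–3, and collect it at the Day 15 laboratory visit already scheduled in those cycles. The date matters: a form completed on Day 9 recalls Days 2–8 (4 of 5 dosing days), and one left until Day 15 covers none.
3. **Section 6.4:** include Day 8 in the by-timepoint, change-from-baseline and maximum-score summaries. State the number of Day 8 forms completed beside the maximum, since the maximum depends on how many were returned. Keep the first Day 1 form as baseline and report later Day 1 forms as recovery measures.

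The cost is an amendment to the schedule of activities, one added analysis timepoint, slight patient burden and some missing forms. Day 8 scores in induction and consolidation will reflect idasanutlin together with chemotherapy; only the maintenance forms reflect idasanutlin alone. Limiting the take-home form to Cycles 1–3 would leave 9 of the 12 maintenance cycles without a dosing-week form, so more cycles should be considered if patients can manage them.
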